Neurocognitive assessment. A battery of tasks designed to measure neurocognitive performance has been developed at the BPRU (Mintzer and Stitzer, 2002) and will be adapted for this study. Functions to be tested include psychomotor speed/pattern recognition (e.g. digit symbol substitution), set shifting/conceptual flexibility (e.g.; trail making tests), divided attention, long-term/episodic memory (e.g. recognition and free recall) and short-term/working memory and focused attention (e.g. N-back task). The Conners Continuous Performance Test will also be used to assess performance in areas of inattentiveness, impulsivity, sustained attention, and vigilance (Epstein et al., 2002).

Inclusion/Exclusion Criteria

Inclusion Criteria:

- Over 18 years old
- Enrolled or meets federal requirements for enrollment in methadone maintenance treatment, and willing to visit the clinic daily
- Evidence of current cocaine dependence (DSM-5 criteria, self-report, urine test positive for cocaine during the intake process or by clinical record during the past 3 months).
- · Willingness to swallow a capsule daily
- Willing to provide observed urine samples three times a week and participate in assessment procedures

Exclusion Criteria:

- Any history of epilepsy or seizure, including alcohol-, sedative-, or cocaine-related seizure;
- Any increased risk of seizure such as serious head trauma with a loss of consciousness of more than an hour duration, brain tumor, or other brain pathology increasing risk of seizure.
- · Current eating disorder including anorexia or bulimia
- Current use (last 30 days) of medication that is contraindicated with bupropion or other bupropion products (e.g. antidepressants, antipsychotics, MAO-A inhibitors, theophyllines, systemic steroids, etc)
- Allergy to bupropion or budeprion
- Liver enzymes greater than 3x ULN
- · Uncontrolled diabetes mellitus, or h/o diabetic coma
- Uncontrolled hypertension with BP > 140/90
- Current psychiatric diagnosis: schizophrenia, psychosis, major depression, mania, current suicidal ideation as determined by MINI psychiatric interview, cognitive impairment severe enough to preclude informed consent or valid responses on questionnaires
- Severe renal insufficiency (eGFR < 30 ml/min)
- Pregnancy or current breast feeding,

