well as any necessary covariates, including cocaine positive vs negative urine tests prior to random assignment as a covariate. Generalized linear mixed models (GLMM) will be used to analyze repeated measures data, since this technique can include participants with incomplete data without resorting to imputation. This approach has been found to minimize bias and maximize power in cases of incomplete follow-up (see Hedden et al, 2009). Data will then be examined using the nonbinary method described by McCann and Li (2012) in which participants who meet an end of study threshold of success (1 week EOS abstinence) are assigned values indicating their number of beyond threshold weeks of success (in our case 1-24). This distribution will be analyzed as a function of drug condition using a two-sided Vander Waerden two-sample test (Permutt and Berger, 2000).

All other analyses will be conducted in the overarching group that includes those abstinent and actively using at baseline. This approach will allow us to preserve all study Aims with a reduced sample size that will ensure the study can be completed in the time allowed.

The data analysis plan consists of the following:

- 1) Comparison of groups for baseline differences. Participants will be compared as a function of medication group on baseline characteristics to determine whether they are comparable with respect to general demographic features, baseline drug use, and reinforcement measures (drug vs. money relative reinforcing potency scale, Snaith-Hamilton Pleasure scale). Groups will be compared using t tests for continuous measures and chi-square tests for categorical characteristics. If medication groups are found to differ on baseline measures, then these characteristics will be used as covariates in subsequent analyses assessing treatment effect.
 - 2) Primary outcome analyses: (see above)
- 3) Secondary outcome analyses: The main secondary outcome measure will be biochemically-confirmed abstinence from opiates. We hypothesize that participants receiving bupropion will have a higher proportion of opiate abstinent samples as well as for cocaine. Analyses conducted to assess the treatment effect for opiate use will be identical to those used for cocaine use (described above).

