- 4) Other Secondary Outcome Analyses: Other secondary outcomes are reinforcement measures, such as the drug vs. money relative reinforcing potency scale, the Snaith-Hamilton Pleasure scale, as well as time engaging in non-drug-related activities and changes in neurocognitive performance. These measures will be collected at baseline and throughout the study. Analyses will be the same as those described for cocaine (GEE with medication group X time as factors). Participants receiving bupropion are hypothesized to find non-drug activities to be more reinforcing than participants receiving placebo, and to engage in more of them.
- 5) Exploratory mediation analysis. Measures collected at baseline including demographic characteristics, intake drug use severity, non-drug reinforcement, non-drug activities and neurocognitive performance will be examined separately to determine whether any predicts outcome independently of treatment. Next, we will add each of these measures to the models that assessed treatment effect, used for primary outcome analyses. If the treatment effect becomes diminished by addition of a third variable, this will be considered preliminary evidence that the third variable may mediate the effect of the treatment.

7. Risks

- a. Medical risks, listing all procedures, their major and minor risks and expected frequency.
- b. Steps taken to minimize the risks.
- c. Plan for reporting unanticipated problems or study deviations.
- d. Legal risks such as the risks that would be associated with breach of confidentiality.
- e. Financial risks to the participants.

Bupropion XL is an FDA-approved antidepressant and smoking cessation pharmacotherapy and will be used in accordance with the prescription labeling instructions during this study. The extended release (XL) preparation allows for once-daily dosing and thus improved adherence. The medication will be titrated to an oral dose of 300 mg after 3 days at 150 mg daily. With a half-life of 21 hours, steady state is

reached after 8 days. Methadone maintenance is a long-standing and effective usual care treatment for opioid dependence but does not directly impact the concurrent use of stimulants alcohol or other drugs.

Risks associated with Bupropion XL side-effects

Major risks of bupropion are summarized below; a complete list of potential side-effects is included in the consent form.

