Responsibility for monitoring data and safety during this clinical trial resides with the Principal Investigator (PI) [name] and co-investigator [name], M.D. AE's and SAE's are generally discovered through careful and frequent monitoring of participants by research and clinical staff using open-ended questions about how the participant has been feeling recently. Any complaint is probed for information about frequency, duration and severity, coded on a side-effects checklist and described in a written summary report. The Principal Investigator coordinates the preparation of semi-annual summary reports on the prevalence of side effects and adverse events observed during the course of the study. These reports will be provided annually to the local IRB and to the NIDA Program Official with the annual progress report. The PI will also be responsible for promptly notifying in writing the local Institutional Review Board if a serious adverse event (SAE) occurs. A SAE is defined as either: death; a life-threatening occurrence; hospitalization; new onset significant medical disorder; or significant exacerbation of an existing medical disorder.

In addition an independent panel of consultants will be contracted for bi-annual review of the risks-benefits ratio of the study. At mid-point during enrollment (when 100 randomized participants have completed the study) this panel will be provided with reports of adverse events and with participant outcome data (urine sample results) by unlabeled medication groups (A vs. B), as a function of study assignment (relapse prevention vs abstinence initiation). This information will be used to assess whether the risks reported are considered to be of unusual magnitude or frequency across any specific groups and to determine whether the study should be ended prematurely due to participant safety concerns. It is unlikely that such a small study would be interrupted because of an uneven distribution of adverse events experienced by any one group, however we will ensure that a qualified panel of reviewers makes this decision.

9. Benefits

a. Description of the probable benefits for the participant and for society.

Study participation will directly benefit participants by providing them with methadone maintenance for opioid dependence, with increased urine monitoring beyond that available in usual care and with contingency management that is likely to reduce the amount of cocaine they use.

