The study will provide important information about the efficacy of bupropion XL for reducing cocaine use in the context of methadone maintenance and background contingency management. The results of this study will provide valuable scientific information regarding the effects of dopamine systems activation on the saliency of non-drug monetary and non-monetary reinforcers as alternative to drug reinforcers. Study findings could also have direct clinical application for combined behavioral and pharmacological treatment of cocaine dependence should the hypotheses be borne out.

10. Payment and Remuneration

Detail compensation for participants including possible total compensation, proposed bonus, and any proposed reductions or penalties for not completing the protocol.

Each participant can earn \$50 for screening, \$210 for 6 longer assessment visits, and up to \$688 in abstinence-contingent incentives based on cocaine negative urine screens for a total of \$948 maximum earnings per participant. Participants can also earn Baltimore City Bus Tokens or be offered other incentives for attendance and/or other study related activities. There are no completion bonuses. Partial payment for study non-completers would be disbursed based on study assessments completed and contingent incentives earned.

11. Costs

a. Detail costs of study procedure(s) or drug (s) or substance(s) to participants and identify who will pay for them.

Participants may be required to pay treatment costs according to policies of the clinical performance site. All research-related costs including study medication and placebo, urine testing and abstinence incentive costs will be supported by the research grant. Any up-front fees associated with new participants entering ATS methadone treatment will be covered by the study.

Literature cited

American Psychiatric Association. (2013). Diagnostic and statistical manual of mental disorders (5th ed.). Arlington, VA: American Psychiatric Publishing.

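### The opiate model names no covariate for methadone status at entry or baseline opiate use, although new and established methadone patients are both enrolled; the comparison is valid but may lose some precision

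*Combined protocol and SAP*

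**What the plan says.** **Who is enrolled.** The inclusion criteria in section 4 accept people who are "Enrolled or meets federal requirements for enrollment in methadone maintenance treatment, and willing to visit the clinic daily", so being on methadone already is not required. Section 9 (Benefits) lists "providing them with methadone maintenance for opioid dependence" as a direct benefit of taking part. Section 11 (Costs) adds: "Any up-front fees associated with new participants entering ATS methadone treatment will be covered by the study". No expected number of new entrants is given.

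**The outcome.** Section 6, item 3: "The main secondary outcome measure will be biochemically-confirmed abstinence from opiates". Section 7 (Risks) states: "Methadone maintenance is a long-standing and effective usual care treatment for opioid dependence".

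**The model.** Item 3 continues: "Analyses conducted to assess the treatment effect for opiate use will be identical to those used for cocaine use (described above". The cocaine model has medication, time and their interaction, as "well as any necessary covariates, including cocaine positive vs negative urine tests prior to random assignment as a covariate". Item 1 compares the arms on "general demographic features, baseline drug use, and reinforcement measures" by t and chi-square tests, and any characteristic on which they differ becomes a covariate.

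**Randomisation.** Section 4 stratifies by response to contingency management only. Randomisation falls in week 3 at the earliest, and at the start of week 6 for those still using cocaine.

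**The concern.** Two kinds of patient enter: those already treated with methadone and those starting it. The plan itself calls methadone effective for opioid dependence, so the two groups may well differ in opiate use at entry and afterwards. A model for opiate abstinence would normally carry a baseline measure related to that outcome. The one covariate named, cocaine urine status, was chosen for the cocaine outcome and is not a measure of baseline opiate use.

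Precision on the main secondary outcome is at stake. If the groups differ, the difference stays in the residual variation, and unequal numbers of new entrants in arms of 50 move the estimate by chance. These are two descriptions of one loss, since the chance shift is already part of the unadjusted standard error. Precision matters more since recruitment problems cut the planned total from 200 to 100 (section 6).

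**Working it through.** **1. The plan's own figure.** Section 6 says 50 per arm is what the power analyses required. It gives no alpha, power or effect size, so the figure cannot be reproduced. It is used below only as the arm size.

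**2. Inputs.** From the documents: n = 50 per arm. Assumed, because the documents give none of them: share of new entrants q = 0.1 to 0.5; gap in opiate-negative proportion between new and established patients D = 0.1 to 0.3; between-person SD within each kind of patient s = 0.35.

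**3. Chance imbalance.** The SD of the between-arm difference in share of new entrants is sqrt(q(1−q) × 2/50).
- q = 0.1: sqrt(0.09 × 0.04) = 0.060
- q = 0.3: sqrt(0.21 × 0.04) = 0.092
- q = 0.5: sqrt(0.25 × 0.04) = 0.100

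By the normal approximation, the arms differ by 10 points or more in about 10%, 28% and 32% of trials respectively. Multiplying the SD by D gives the shift in the opiate difference: 0.6 points (0.060 × 0.1) to 3.0 points (0.100 × 0.3) at one SD.

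**4. Variance inflation without adjustment** = 1 + q(1−q)D²/s², with s² = 0.1225.

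| q | D | q(1−q)D² | Inflation | Power if 80% when adjusted |
|---|---|---|---|---|
| 0.1 | 0.1 | 0.0009 | 1.007 | 80% |
| 0.2 | 0.2 | 0.0064 | 1.052 | 78% |
| 0.3 | 0.3 | 0.0189 | 1.154 | 74% |
| 0.5 | 0.3 | 0.0225 | 1.184 | 73% |

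At q = 0.3 and D = 0.3 the standard error is sqrt(0.04 × 0.1414) = 7.5 points unadjusted and sqrt(0.04 × 0.1225) = 7.0 points adjusted. The 95% half-widths are 14.7 and 13.7 points.

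**5. Validity.** Simulation under no treatment effect (normal model, 4,000 trials per scenario) at (q, D) = (0.2, 0.2), (0.3, 0.3) and (0.5, 0.3) gave unadjusted type I error of 0.050, 0.044 and 0.049. With adjustment it was 0.050, 0.047 and 0.048. Leaving the covariate out does not produce false positives.

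**6. Does the baseline-difference rule close the gap?** Methadone status is not on the comparison list. Suppose it were tested at an assumed two-sided 5% level with q = 0.3. Significance then needs a gap of about 1.96 × 0.092 = 18 points. By exact binomial calculation, the arms differ by 10 points or more in 33% of trials, and in 28% of trials such a gap exists but is not significant, so no adjustment would follow.

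The formulas in steps 3 and 4 treat each person's proportion of opiate-negative samples as a continuous outcome. The plan uses a repeated-measures logistic model, where adding a predictive covariate also changes the odds ratio being estimated. The figures therefore indicate scale only.

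**The case against.** **A reader might infer that the opiate model cannot adjust for this at all.** It can. It inherits the open covariate clause and the baseline-difference rule, and baseline drug use is on the comparison list. That stands. But both routes depend on the data, neither names methadone status, and step 6 shows how often a test-based rule would miss a sizeable gap.

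**A reader might infer that methadone induction carries into the randomised period and distorts the bupropion comparison.** The documents do not show this. They give no induction length, no time course of opiate use and no methadone start date relative to study week 1. Some two to five weeks of lead-in come before randomisation. Nor would such carry-over bias a randomised comparison. For the same reason, nothing in the documents supports preferring methadone status to a baseline opiate urine, which is the more natural covariate.

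**A reader might infer a large gain.** A gain of 15% to 21% more participants needs 30% new entrants, a 30-point gap and an SD of 0.30 to 0.35 (0.0189/0.1225 and 0.0189/0.09). Section 4 schedules cocaine urines three times a week but only a periodic full drug screen, so opiate results may be sparser and noisier. With SD 0.45 the same case gives 0.0189/0.2025 = 9%. With 10% new entrants, a 20-point gap and SD 0.35 it is 0.0036/0.1225 = 3%. The fee sentence concerns one clinic among several sites and gives no count.

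It is also fair to say that dose or site could be proposed as covariates on similar reasoning. Methadone status differs in that the eligibility rule itself creates the two groups.

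**Conclusion.** The point holds as a minor matter of precision on a secondary outcome. The plan knowingly mixes new and established methadone patients, and pre-specifies neither methadone status nor baseline opiate use in the opiate model. The unadjusted comparison is unbiased and its type I error is preserved. Under the assumptions in step 2, the loss runs from negligible (variance up 0.7%) to moderate (up 18%, power 73% instead of 80%). Where the trial falls in that range depends on the number of new entrants and their opiate-negative rate, neither of which is given.

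**What to change.** In section 6, item 3, add a sentence along these lines: the regression model for opiate abstinence will include, as pre-specified main-effect covariates, methadone status at study entry (new versus established) and opiate urine result at screening; the number of new entrants will be reported by arm.

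The eligibility check and clinic record should supply methadone status. The screening urine covers cocaine and other drugs (section 4, Screening measures); the sentence should confirm that opiates are on that panel. The two-sample rank test that item 3 also inherits takes no covariates and stays unadjusted.

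A status-by-time interaction should be at most a sensitivity analysis. The plan does not say whether time is continuous. If it is categorical, the interaction adds a term for each further time point and could be unstable in a logistic model with few new entrants.

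The cost is a sentence in the plan and one or two model terms. If few new entrants enrol, the gain from methadone status is negligible.
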